#### 4.8.2 Withdrawal

A participant can withdraw from the trial at any time. Withdrawal indicates that the participant no longer wishes to take the study drug and that he/she does not agree to ongoing follow up of any kind (including telephone follow-up, emailed questionnaire and electronic linkage). There is no obligation for a participant to provide signed confirmation of his/her withdrawal. Information collected about the participant up to the date of withdrawal will still be retained and analysed but no further data will be sought or stored from that date forwards.

## 4.9 ANALYSIS OF BLOOD AND URINE SAMPLES

No biological samples will be retained or stored during the trial for research purposes. All blood and urine samples for assessing eligibility and for research purposes taken at the screening visit and randomisation visit will be sent to the LCC's local NHS hospital biochemistry laboratory for analysis. These samples will be discarded or destroyed by these laboratories according to their standard operating procedures. LCCs will be responsible for deciding how many blood samples need to be sent to their local laboratory for the required analyses in accordance with their laboratory policy. Typically, this will be two whole blood samples (one gel tube for renal function, LFTs, CK, and lipid profile [hours since last meal will be recorded; there is no requirement to fast]; one EDTA tube for HbA1c analysis) and one spot urine sample (in plain tube) at the screening visit; and this will be followed by one blood sample (one gel tube for renal function, LFTs, CK) at the randomisation visit which again does not require fasting. All relevant NHS laboratories have Clinical Pathology Accreditation according to International Standard for Organisation 15189 and currently perform regular quality control procedures for the routine assays in question. Biochemistry results taken at the screening and randomisation visits will be transferred to the TMS via two routes: either by LCC staff manually entering the data directly into the eCRF or by linkage to the SCI Diabetes registry and uploading the data.

Unplanned visits to local sites by participants after randomisation can be arranged by the CCO, RCC or LCC for the purposes of biochemistry safety testing if this is felt necessary to determine the safety of ongoing treatment with the study drug.

## 4.10 END OF TRIAL

The trial will continue until at least 222 primary events have occurred and until median follow-up is at least 4 years, whichever is the later. The 'end of study' is defined as the date on which the trial database is locked for the primary analysis. The Trial Steering Committee (TSC) has the right to terminate the study for clinical or administrative reasons at any time.

The end of the study will be reported to the REC and Regulatory Authority within 90 days, or 15 days if the study is terminated prematurely. Investigators will notify participants and inform them of appropriate procedures to follow. A summary report of the study will be provided to the REC and Regulatory Authority within one year of the end of the study.

## 4.11 TRIAL MEDICATION

### 4.11.1 Name and description of investigational medicinal product(s) (IMP)

IMP name:	Lipantil Supra 145 mg film coated tablet [fenofibrate (nanoparticles) 145 mg].
Marketing Authorisation Holder:	Mylan IRE Healthcare Limited, [name]
Marketing Authorisation Number:	PA 2010/015/003

The IMP to be used in LENS is fenofibrate in the form of 145mg film-coated tablets with a nanoparticle formulation. The control will be a matching placebo tablet. The marketing authorisation for this formulation of fenofibrate is held by Mylan in the Republic of Ireland and other member states of the European Economic Area (EEA) though not in the UK. Study IMP and matching placebo tablets will be supplied in bulk form by Mylan free of charge.

### 4.11.2 Legal status of the drug

Fenofibrate is a licensed drug in the UK to treat “mixed hyperlipidaemia if statin contra-indicated or not tolerated, or in severe hypertriglyceridaemia; or as an adjunct to statin in mixed hyperlipidaemia if triglycerides and HDL-cholesterol inadequately controlled in patients at high cardiovascular risk”. In LENS the drug will be used outside these indications, and we will use a formulation currently in use elsewhere in the EU which is bio-equivalent to doses used in the UK. Notably, Australia and Singapore have licensed fenofibrate for participants with DR, the same group to be studied in LENS.

### 4.11.3 Summary of Product Characteristics (SmPC)

The relevant section of the SmPC for fenofibrate will be used as the Reference Safety Information during the trial for pharmacovigilance reporting purposes. The sponsor will periodically check (at least once a year) for any changes to the licensing status of fenofibrate.

### 4.11.4 IMP preparation, storage, labelling and supply

IMP will not be issued to study participants at face-to-face study clinic visits, instead all study treatment will be issued from a central location and sent to study participants, on instruction from the CCO, via a mailing service.

Two different types of packaged study IMP will be used (see Table 4 below).

- **Run-in Treatment** will be issued and sent to consenting participants after the initial Screening visit (once confirmed eligible by their blood results) to be taken during the pre-randomisation Run-in phase of the trial.
- **Randomised Treatment** will be sent to participants following their Randomisation visit, new supplies sent at approximately week 22 post randomisation and at 26-weekly intervals thereafter. Participants will be sent a Randomised Treatment pack (Type A or Type B; see Table 4) corresponding to their most recently recorded renal function.

**Table 4.** Run-in treatment and randomised treatment to be used in LENS

Treatment Dose	Run-in treatment	Randomised treatment
fenofibrate 145mg (open label)	One pack containing 70 tablets	n/a
fenofibrate 145mg OR placebo (double blind)	n/a	Type A pack containing 180 tablets (for participants with most recent recorded eGFR of $\geq 60/\text{mL}/1.73\text{m}^2$ )
fenofibrate 145mg OR placebo (double blind)	n/a	Type B pack containing 90 tablets (for participants with most recent recorded eGFR 30-59mL/min/1.73m  )

Mylan will provide tablets of fenofibrate and matching placebo in bulk form. Batches of tablets will be delivered according to an agreed schedule and in agreed quantities to the trial's contract packager (details below):

Contract packaging company:	AndersonBrecon (UK) Limited
Address:	[name]
Authorisation number:	MIA(IMP) 11724

Under the direction of the CCO the contract packager will be responsible for:

- packaging, labelling and QP release of uniquely identifiable packs of finished study IMP in accordance with EU Good Manufacturing Practice (GMP) standards
- storage of released packaged IMP
- selection and preparation for despatch of specified bottles of packaged IMP assigned to specified study participants

Royal Mail (along with other third party mailing/courier service provider(s) if required) will be responsible for delivering packs containing specified bottles of packaged IMP assigned to specified study participants. All packs of study IMP sent to study participants will be sent by routine post. At the time of mailing out IMP (including both run-in packs and post randomisation packs), participants will receive an automated text or email informing them that their study treatment is *en route* and to contact the CCO if the study treatment does not arrive safely.

Design and formatting of IMP labels required for the two types of Treatment Bottle will be the primary responsibility of the contract packager in collaboration with the CCO. All IMP labels will be designed in accordance with Annex 13 of the EU GMP Guide.

The CCO will maintain an inventory and audit trail of all bottles of study IMP on the TMS that have been requested, packaged, assigned and sent to participants, returned by participants and destroyed. In addition, the TMS will record any bottles of study IMP that have expired or been damaged prior to being assigned to study participants as well as a record of their subsequent destruction.

Participants will be advised to store study IMP at room temperature (Store below 30°C).

All bottled study IMP will be labelled with an expiry date beyond which it should not be used, and will only be issued to participants with due allowance for the remaining shelf life.

Participants will be asked to return unused Run-in drug to the LCC at the time of the Randomisation visit and the LCC will be responsible for its handling and destruction. When required, study participants will be advised to take any expired or unused study IMP to a local pharmacy for safe disposal. This goes against normal practice for return and accountability of IMP in standard clinical trial settings. However, due to the streamlined design of the LENS trial, where participants will not attend routine clinics during the follow-up phase of the trial, it has been deemed to be too problematic and prone to unacceptable risk to expect study participants to securely return study IMP via the postal system or other courier service.

The CCO will be responsible for handling and destruction of any returned, expired or unused IMP and packaging materials which it may receive back from study participants or that is returned as undelivered. Likewise, LCCs will be responsible for handling and destruction of any returned, expired or unused IMP and packaging materials which are handed in to them.

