#### **4.5.3 Activities after the screening visit including local PI sign-off of eligibility**

Along with the signed ICF, the LCC research nurse will upload a copy of the detailed PIL to the health board's clinical portal (i.e. electronic health record) to enable clinicians involved in the patient's care to be aware of, and gain further information about, the trial. In health boards which use paper records, the detailed PIL will be filed in the patient's case notes.

When the results of blood biochemistry (renal function, liver function tests [LFT], CK), HbA1c, random lipid profile [including at least total cholesterol, HDL-cholesterol and triglycerides]) are available these will be transcribed into the TMS and a further assessment made of the patient's eligibility. Urine biochemistry results will be obtained subsequently as part of SCI Diabetes data linkage. Local laboratory ULNs will be used for LFTs and CK and these will be entered into the eCRF. Local lab ULNs are not required for renal function, lipids, HbA1c. Validation queries will highlight clear errors and data will be obtained from SCI Diabetes at regular intervals (every 6-12 months) to retrospectively verify the accuracy of the transcribed data.

Based on the details collected at the screening visit and following receipt of the screening biochemistry results, eligibility for participating in LENS will be determined according to the eligibility criteria. This will be recorded electronically on the eCRF. Both patients and their GPs will be written to if their screening blood test results indicate that they are not eligible to enter the trial to explain this. For those patients who remain eligible, the local PI or a doctor to whom responsibility has been delegated will be required to sign off their eligibility. This sign-off will approve the participant to enter the run-in phase and to be randomised after the run-in if their biochemistry results at the Randomisation visit are within pre-specified limits (see below) (also termed an 'order-to-supply'). This approval will be in the form of an electronic signature on the trial eCRF. The local PI or delegated doctor's electronic sign-off will remain valid for the entire trial unless the clinical condition of the patient requires a reduction in dose or cessation of the study drug after randomisation. The 'order-to-supply' will be an inbuilt part of the eCRF.

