#### **4.6.3 Modifying study treatment**

It is well established that fenofibrate leads to an increase in serum creatinine, typically by 10-20%. Lower doses of fenofibrate are recommended in those with chronic kidney disease. It is therefore expected that some trial participants initially taking one tablet daily will need to reduce their dose of study drug based on renal function in routinely collected blood tests.

During follow-up, renal function (based on routinely collected blood tests done at the discretion of each participant's GP and/or hospital doctor) will be monitored for safety in almost 'real time' using a bespoke SCI Diabetes domain created by SCI Diabetes. This will enable an experienced study doctor at the RCC to identify any LENS participants who cross pre-specified eGFR thresholds (namely 30 and 60mL/min/1.73m^2 respectively) within days of this occurring. To achieve this, the study doctor will perform an automated search of SCI Diabetes for any renal function blood results for all LENS participants approximately every 2 weeks. Participants whose Randomisation visit eGFR was  $\geq 60\text{mL/min}/1.73\text{m}^2$  (and who are therefore initially prescribed one study tablet daily) but whose on-treatment eGFR subsequently falls to 30-59mL/min/1.73m^2 in routinely collected blood tests will be asked to reduce study drug to one tablet every second day and no increase in dose frequency (i.e. back to one tablet daily) will be permitted thereafter. The LCC's local PI or LCC doctor with delegated responsibility or experienced CCO doctor will be required to electronically sign an updated 'order to supply' to record any such change. Participants whose on-treatment eGFR falls below 30mL/min/1.73m^2 will be asked to discontinue study drug therapy. Participants who experience a transient worsening in renal function due to a self-limiting illness (e.g. gastro-enteritis) during which study treatment has been stopped will be able to restart study medication subsequently in accordance with their renal function.

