#### **4.11.7 Dosage modifications**

Participants whose Randomisation visit eGFR (i.e. after open-label treatment with fenofibrate) is  $\geq 60\text{mL/min}/1.73\text{m}^2$  and whose eGFR falls to  $30\text{--}59\text{mL/min}/1.73\text{m}^2$  thereafter while on randomised study treatment will be required to reduce study drug to one tablet every second day (see section 4.6.3). The local PI or clinician with delegated responsibility or experienced CCO clinician will be required to electronically sign an updated 'order to supply' to verify this. Participants whose eGFR falls below  $30\text{mL/min}/1.73\text{m}^2$  will be asked to discontinue study drug therapy (see section 4.6.3). Dosage will not be reduced based on patient request alone. Participants who experience a transient worsening in renal function due to a self-limiting illness (e.g. gastro-enteritis) during which study treatment has been stopped will be able to restart study medication in accordance with their renal function.

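### Protocol 4.11.4 and Table 4 choose the pack by the latest eGFR alone, which assigns the daily pack to some participants whom 4.6.3 bars from returning to daily dosing

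*Protocol*

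**What the plan says.** Protocol 4.11.4 describes two randomised packs and has the participant sent the one "corresponding to their most recently recorded renal function". Table 4 sets the criteria. Type A, with 180 tablets, is "for participants with most recent recorded eGFR of" at least 60 mL/min/1.73m². Type B, with 90 tablets, is for a latest value of 30-59. The first pack follows the randomisation visit, with "new supplies sent at approximately week 22 post randomisation and at 26-weekly intervals thereafter". Packs leave the central location "on instruction from the CCO".

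Protocol 4.6.3 sets the dosing rule. A participant randomised at 60 or above whose on-treatment eGFR falls to 30-59 moves to one tablet every second day, and "no increase in dose frequency (i.e. back to one tablet daily) will be permitted thereafter". Below 30, study drug is discontinued. Both 4.6.3 and 4.11.7 add that a participant whose treatment was stopped during a transient worsening from a self-limiting illness may restart according to renal function.

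On authorisation, 4.11.7 says that a clinician "will be required to electronically sign an updated" order to supply when the dose is reduced; 4.6.3 says the same. Under 4.5.3 the sign-off stays valid for the whole trial "unless the clinical condition of the patient requires a reduction in dose or cessation of the study drug", and the order "will be an inbuilt part of the eCRF".

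**The concern.** The dosing rule depends on history: once reduced, a participant stays reduced. The pack rule has no memory and looks only at the latest value. The two must diverge for anyone who was reduced and later records 60 or above, and 4.11.4 neither makes an exception nor refers to 4.6.3 or to the signed order. The bar on going back to daily dosing appears only in 4.6.3. Section 4.11.7 repeats the reduction and cross-refers to 4.6.3 but does not restate the bar, and 4.11.5 gives dosing by renal function without it.

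The situation is foreseeable. Section 4.6.3 expects some participants on daily dosing to be reduced on routine blood results, and it allows temporary breaks from treatment. It puts the typical creatinine rise on fenofibrate at 10-20%, and 4.11.6 describes that rise as reversible. A reduced participant close to 60 could therefore record a later value above it. At stake is whether someone instructed to take a tablet every second day is posted a pack sized for daily use. No visits are planned after randomisation (4.6.2), and compliance is self-reported every six months (4.11.13), so the protocol describes no routine tablet count that would show a mismatch.

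**Working it through.** The plan gives no figure to reproduce. The check sets the two rules side by side, after confirming that pack type stands for dosing regimen.

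**Pack type and regimen.** Inputs: 180 and 90 tablets (Table 4); 26-week supplies (4.6.1 and 4.11.4).

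- Supply period: 26 × 7 = 182 days.
- Type A: 180 / 182 = 0.99 tablets per day, a daily supply.
- Type B: 90 / 182 = 0.49 tablets per day, an every-second-day supply.

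**The two rules applied to illustrative eGFR sequences** (first value at randomisation; the values are assumptions chosen to fall either side of the thresholds):

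| Sequence | 4.11.4 and Table 4 | 4.6.3 | Result |
|---|---|---|---|
| 62, 65 | Type A | Daily (Type A) | Agree |
| 62, 57 | Type B | Every second day (Type B) | Agree |
| 62, 57, 61; dose reduced at 57 | Type A | Every second day (Type B) | Conflict |
| 62, 57, 61; treatment stopped at 57 for a self-limiting illness, then restarted | Type A | Restart by renal function (Type A) | Agree |
| 62, 28 | No pack listed | Discontinue | No conflict |
| 55, 61 | Type A | Bar not worded for this group | Not settled |

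The conflict is confined to the third row. The last row is a neighbouring gap. The bar in 4.6.3 is written for participants randomised at 60 or above and says nothing of those randomised at 30-59 who later rise, while Table 4 would move them to Type A. Section 4.5.3 foresees a changed sign-off only for a reduction or cessation.

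**Size of the mismatch.** A Type A pack taken every second day lasts 180 × 2 = 360 days, against 90 × 2 = 180 days for Type B. The rule is re-applied at each repeat dispatch while the latest value stays at 60 or above. How many participants would be reduced and then recover cannot be derived from either document.

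**The case against.** The strongest reply is that 4.11.4 deals with supply and 4.6.3 with dose. On ordinary reading the specific bar prevails over a general description of pack sizes, so the intended dose is not in doubt. That is right about intent. It does not make the supply rule correct as written, because the packs are sized to the two regimens.

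A second reply is that controls exist. A reduction needs a newly signed order, the order sits in the eCRF, dispatch needs an instruction from the co-ordinating office, and the trial management system keeps an audit trail of the packs assigned and sent (4.11.4). These may well stop a wrong mailing. But 4.11.4 does not tie pack choice to the order, so the safeguard works only if the written pack rule is not followed literally.

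A third reply is that little follows clinically, and this largely stands. Both packs hold the same 145mg tablets, and a wrong pack first of all means surplus tablets. The conflict arises only when the latest eGFR is at least 60, where daily dosing is the protocol's standard. Section 4.11.6 describes the trial's thresholds and doses as more conservative than the BNF, and renal results are searched about every two weeks (4.6.3).

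A reader might infer that participants are being sent, or are taking, the wrong dose. The documents do not support that: they do not describe the supply system's logic, and they show no wrong dispatch. A reader might also take every return to 60 or above as a conflict. The transient-illness clause rules that out where treatment was stopped for the illness.

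**Conclusion.** The inconsistency is real and minor. Two current sections of the protocol give different answers for one group: participants randomised at eGFR 60 or above, reduced under 4.6.3 other than by a treatment stop for a transient self-limiting illness, and later recorded at 60 or above. For them the supply rule assigns a daily pack that the dosing rule forbids. The conclusion rests on reading 4.11.4 and Table 4 as written and on treating pack type as matched to regimen, which the tablet counts support. It assumes nothing about how dispatch works in practice. The number affected is unknown. It bears on the consistency of a dosing safety rule; it has no bearing on sample size, power or the primary analysis.

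**What to change.** - Add a sentence to 4.11.4 and a footnote to Table 4: a participant whose dose frequency was reduced under 4.6.3 stays on Type B whatever the later eGFR, in line with the current signed order-to-supply.
- State the exception in the same place: a restart after a transient illness during which treatment was stopped follows renal function, as 4.6.3 and 4.11.7 already allow.
- State separately which pack applies to participants randomised at eGFR 30-59 who later record 60 or above. Linking packs to the signed order would otherwise change this group's supply without saying so.
- Check once that the supply system applies these rules. The existing audit trail of packs would also show whether a Type A pack was ever sent after a reduction.

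The cost is a few lines of text and one check, with no new procedures or data collection.

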#### **4.11.5 Dosage schedules**

The dose of fenofibrate tablets is 145mg in nanoparticle formulation. After randomisation, study drug will be taken orally as one tablet daily (in the context of normal renal function i.e. eGFR  $\geq 60\text{mL/min}/1.73\text{m}^2$ ) or one tablet every second day (in the context of chronic kidney disease with eGFR 30-59mL/min/1.73m^2). Study drug can be taken with or without food.

Doses of fenofibrate used in earlier trials were 200mg daily (micronised) in FIELD and 160mg daily in ACCORD-Lipid. The selected formulation and dose for LENS is bio-equivalent to the doses used in FIELD and ACCORD-Lipid. Intermittent dosing is frequently used in clinical practice for other clinical conditions (e.g. vitamin D in chronic kidney disease). Given the lack of availability of lower dose fenofibrate tablets for LENS and, in the context of data suggesting that fenofibrate treatment may in fact be beneficial for patients with chronic kidney disease, intermittent dosing for those with chronic kidney disease represents a suitable option. No further study drug will be provided after the completion of the trial.

